### 3.2.1 Dose Limiting Toxicities

The rate of entry and escalation to the next dose level will depend upon assessment of the toxicity profile of patients entered at the previous level. Acute toxicity will be assessed up to and including 3 months following the final fraction of radiotherapy (i.e. at C6D1). The MRC dyspnoea score (Appendix 2) will be used to assess dyspnoea at baseline/on treatment and the National Cancer Institute Common Toxicity Criteria for Adverse Events (NCI CTCAE) version 4.0 will be used to grade all drug and lung SBRT observed toxicities (Appendix 4). The SRC will consider dose escalation once the 3rd or 6th patient in the cohort has completed the DLT period and review the toxicities before recruitment to the next dose level can begin or the cohort is expanded to 6 patients.

Any DLT must be a toxicity that is considered probably, possibly or definitely related to the combination of pembrolizumab and lung SBRT. DLT is defined as follows:

## **Haematologic:**

- Neutropenia with fever grade  $\geq 3$
- Thrombocytopenia with bleeding grade  $\geq 3$

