### **2.1 Study Objectives & Hypothesis**

#### **2.1.1 Primary Objective & Hypothesis**

- Objective: To assess the safety and tolerability of lung SBRT with pembrolizumab and to determine the RP2D of lung SBRT to be used in combination with pembrolizumab.
- Hypothesis: Lung SBRT can be safely administered in combination with pembrolizumab without significant DLTs.

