In the dose escalation phase, a minimum of 3 patients will be required per dose level being assessed. A minimum gap of 1 week will be left between the treatment of the first and the second, and between the second and the third patients with the combination of pembrolizumab and lung SBRT to mitigate against multiple patients suffering from acute toxicity. The DLT period for this study is 12 weeks from the last dose of lung SBRT (i.e. at C6D1). The dose escalation will be considered by the Safety Review Committee (SRC) once the 3rd or 6th patient in the cohort has completed the DLT period. If no DLT is observed at a dose level,

then lung SBRT will be dose escalated to the next dosing level (see Table 1). If 1 out of 3 patients experience a DLT, then the cohort will be expanded to 6 patients. If 1 in 6 patients experience a DLT, then the dose will be escalated to the next dosing level. However, if  $\geq 2$  in 6 patients experience a DLT then the maximum administered dose (MAD) will have been reached, and the RP2D will be the previous dosing level that will be used for the dose expansion cohorts. If the MAD is seen at dose level 1 then the study will be terminated. While waiting for 3 or 6 patients to complete the DLT period, no additional patients will be recruited. Further patients can only be recruited after the SRC has reviewed the toxicity data for the cohort and taken a decision to dose escalate to the next cohort or expand the current cohort to 6 patients.

Once the MTD has been determined the trial enters the dose expansion phase (unless the MTD is dose level 1). Here, 12 patients will be treated with the RP2D of SBRT combined with pembrolizumab.

If there is ongoing clinical benefit at 24 months, the CI/PI will need to discuss with the sponsor and MSD, on a case by case basis for the continuation of pembrolizumab.

**Table 1:** Lung SBRT dose levels and pembrolizumab dosing during the dose escalation and dose expansion phase.

Dose Level	Pembrolizumab Dose	Lung SBRT to part of a lung lesion
1	200 mg i.v. over 30 minutes, every 3 weeks	30 Gy in 3# (Monday, Wednesday, Friday)
2	200 mg i.v. over 30 minutes, every 3 weeks	54 Gy in 3# (Monday, Wednesday, Friday)
Dose expansion	200 mg i.v. over 30 minutes, every 3 weeks	RP2D

SBRT: Stereotactic Ablative Body Radiotherapy; Gy: Gray; i.v.: intravenous; mg: milligrams;  
RP2D: Recommended Phase 2 Dose; #: fraction.

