## **Non-Haematologic:**

Any NCI CTCAE  $\geq 3$  grade non-haematological toxicity that is definitely, probably or possibly related to the combination of pembrolizumab and lung SBRT including the following:

[figure not shown]
- Increased MRC dyspnoea score  $> 2$  grades from baseline and/or acute dyspnoea grade  $\geq 4$  (or CTCAE dyspnoea grade  $\geq 3$ ) persisting for  $> 7$  days (including weekend).
- Pneumonitis/pulmonary infiltrates grade  $\geq 3$  persisting for  $> 7$  days (including weekend).
- Oesophagitis grade  $\geq 3$  persisting for  $> 7$  days (including weekend).
- Toxicity leading to interruption of radiotherapy for  $> 7$  days (including weekend).

Escalation to the next dose level will not proceed until the following criteria are satisfied by the SRC:

- If 0 out of 3 patients experience a DLT, escalation to the next dose level can proceed.
- If 1 out of 3 patients experiences a DLT, a further 3 patients will be recruited at that dose level.
  - If 1 out of 6 patients experiences a DLT, then escalation to the next dose level can proceed.
  - If  $\geq 2$  out of 6 patients experience a DLT, the MAD will have been reached. The RP2D will be the dose level prior to when the DLTs were observed or dose level 2 if no DLTs were observed.  
All patients in the expansion cohort will have lung SBRT dosed at the RP2D (see Figure 1).
- If 2/3 patients experience a DLT then the MAD will have been reached and the expansion cohort phase will begin at the previous dose level unless this occurs at dose level 1.
- If dose level 1 is not tolerated due to DLTs, the expansion cohort will not go ahead and the trial will be terminated.

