### 4.3 Patient Replacement Strategy

Additional patients may be enrolled in a given cohort to ensure that the required number of evaluable patients in each cohort is achieved. A patient that discontinues the trial for progressive disease within 3 months of the last dose of radiotherapy will not be evaluable for DLTs and therefore will need to be replaced. A patient that discontinues the trial for a drug-related AE will not be replaced and will be counted in the evaluable population of patients for the respective cohort. However, patients found to have active

pneumonitis on C1D1 of pembrolizumab or day 1 of radiotherapy will be removed from the trial and can be replaced. Also patients who do not reach follow-up 3 months post completion of lung SBRT for reasons other than progression or toxicity can be replaced by new patients in that cohort to ensure there is a minimum of 3 (or 6 if required) patients in each cohort.

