### **8.1.4 Timing of analyses**

Toxicity data will be reviewed by the Safety Review Committee prior to any decision regarding dose escalation or opening of new dose cohorts.

Part A can be analysed once the last patient in cohort 2 has completed the DLT period which is 12 weeks from the last dose of lung SBRT (i.e. at C6D1). For parts A and B, end of treatment is until disease progression, or unacceptable toxicities, or the patient withdraws consent to the trial or when patient has completed 24 months of treatment. End of study is when the last patient has completed the off-study or the final follow-up visit, whichever happens last.

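### Section 3.2.1 does not count a related Grade 4 haematological event as a DLT unless it comes with fever, bleeding or a related Grade 3+ non-haematological toxicity

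*Combined protocol and SAP*

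**What the plan says.** Section 3.2.1 defines DLTs in two lists. The haematological list has two entries, neutropenia with fever and "Thrombocytopenia with bleeding grade", each at Grade 3 or higher. The non-haematological list opens with a catch-all for any CTCAE Grade 3 or higher "grade non-haematological toxicity that is definitely, probably or possibly related to the combination of pembrolizumab and lung SBRT". No entry covers anaemia, haemolysis, marrow failure or a cytopenia without fever or bleeding.

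The escalation rule is written in DLT counts: "Escalation to the next dose level will not proceed until the following criteria are satisfied by the SRC", and then "If 0 out of 3 patients experience a DLT, escalation to the next dose level can proceed". One DLT in three expands the cohort to six; one in six allows escalation; two or more is the maximum administered dose. Section 8.1.1 takes the proportion of patients with a DLT, with an exact 95% interval, as the primary toxicity rate, and separately tabulates all toxicities by type, grade and dose level.

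On evaluability, Section 4.3 says: "A patient that discontinues the trial for a drug-related AE will not be replaced and will be counted in the evaluable population of patients". The primary hypothesis in Section 2.1.1 concerns the combination: "Lung SBRT can be safely administered in combination with pembrolizumab without significant DLTs".

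Elsewhere the protocol treats the omitted events as serious. Table 12 lists autoimmune haemolytic anaemia, aplastic anaemia, TTP and any Grade 4 anaemia as events of clinical interest. Table 8 (its row for other drug-related toxicity) and the haematologic rows of Appendix 5 stop pembrolizumab at Grade 4.

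**The concern.** The ordering is uneven. A related Grade 3 non-haematological toxicity falls under the catch-all, while a related Grade 4 haematological event, which Appendix 4 grades as life-threatening, may fall under nothing. With three to six patients per level, one classification can decide whether a level reads 0/3 or 1/3, or 1/6 or 2/6. At dose level 2 that count also decides whether 54 Gy becomes the recommended dose for the 12 expansion patients. The primary proportion would then omit an event that bears directly on the safety of the combination.

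**Working it through.** **Reproducing the plan's figure.** Section 8.2: 3 × 2 levels = 6 minimum, 6 × 2 = 12 maximum, and 12 + 12 in expansion = 24. This agrees. The plan states no target DLT rate, so there is no operating characteristic to check it against.

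**Does any other wording catch the event?**
- The item on radiotherapy interrupted for more than 7 days sits in the non-haematological list, and SBRT lasts 5 days (Appendix 3). Read loosely it might catch an event that delays a fraction, but it does not close the gap.
- One figure in the non-haematological list was not readable in the copy examined. Given its place, nothing suggests that it adds a haematological criterion.
- An event that also causes a related Grade 3+ non-haematological toxicity is already a DLT and lies outside this point.

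**Inputs for size.** The rule is from Section 3.2.1. The documents give no rate of such events under the combination. For pembrolizumab alone, Section 1.1.4.2 names only pneumonitis and severe skin reactions as Grade 3-5 immune-related events at 1% or more, and the list of rarer events in Section 6.5 names none that is haematological. Assumed: h = 0.5%, 1% or 2% for the events that the fix would count, and b = 5%, 10% or 20% for DLTs already counted.

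**Probability of escalating from a level.** A level passes with 0/3, or with 1/3 followed by 0/3:

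P(p) = (1−p)³ + 3p(1−p)⁵

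As written, p = b. With the events counted and independent of other DLTs, p = 1 − (1−b)(1−h).

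Example, b = 10%, h = 1%: as written 0.9³ + 0.3 × 0.9⁵ = 0.729 + 0.177 = 0.906. Counted, p = 1 − 0.90 × 0.99 = 0.109, which gives 0.707 + 0.184 = 0.891. The difference is 1.5 points.

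| b | As written | h = 0.5% | h = 1% | h = 2% | Fall (points) |
|---|---|---|---|---|---|
| 5% | 0.973 | 0.969 | 0.963 | 0.952 | 0.49, 1.02, 2.17 |
| 10% | 0.906 | 0.899 | 0.891 | 0.875 | 0.75, 1.52, 3.11 |
| 20% | 0.709 | 0.700 | 0.691 | 0.674 | 0.87, 1.74, 3.48 |

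If the two rates simply add (p = b + h), the falls are slightly larger: 1.7 points at 10% and 1%, and 4.4 points at 20% and 2%.

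**Chance that it arises.** 1 − (1−h)ⁿ at h = 1% is 3.0% in 3 patients, 5.9% in 6 and 11.4% in 12. At h = 2% it is 5.9%, 11.4% and 21.5%.

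**If one event occurs in the first three patients with no other DLT.**
- As written: 0/3, exact 95% interval 0 to 70.8%; the criterion for escalation is met.
- Counted: 1/3, interval 0.8% to 90.6%; escalation then needs no DLT in three more patients, with probability (1−p)³ = 0.857, 0.729 or 0.512 at a true rate of 5%, 10% or 20%.

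**If one event occurs in a cohort of six with one other DLT.** As written 1/6 (0.4% to 64.1%), escalate. Counted 2/6 (4.3% to 77.7%), maximum administered dose reached.

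**The case against.** The strongest reply is that the SRC already deals with this. Section 3.2 says "Further patients can only be recruited after the SRC has reviewed the toxicity data for the cohort and taken a decision to dose escalate", and the sentence goes on to allow expansion to six as the alternative, without tying that choice to a DLT. Section 8.1.4 adds: "Toxicity data will be reviewed by the Safety Review Committee prior to any decision regarding dose escalation or opening of new dose cohorts". A life-threatening event is an SAE, reported within 24 hours (Section 7.4.1), and the SRC reviews all SAEs (Section 10.9). Section 3.5.1, item 3, permits termination on the incidence or severity of adverse drug reactions. All of this stands. It means that the event is neither hidden nor beyond action. It does not put the event into the count: no text lets the SRC reclassify a non-DLT or add it to the primary proportion.

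Second, evaluability is less clear-cut for some patients. Section 4.3 speaks of leaving the trial, whereas Table 8 and Appendix 5 only stop the drug. Section 8.1 sets aside for separate description those who do not complete the required safety observations, so a patient who dies or drops out within the window may not be a plain evaluable non-DLT. That stands, and the point is limited accordingly. A haematological death without infection, bleeding or organ failure is also close to an empty set.

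Third, only the SBRT dose escalates, so restricting haematological DLTs to complicated cytopenias is a defensible choice. This has force for brief asymptomatic neutropenia or thrombocytopenia. It has less for haemolysis, marrow failure or TTP, because both the hypothesis and the relatedness test refer to the combination.

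**Conclusion.** The gap is real and narrow. As written, a related isolated Grade 4 haematological event outside the two listed forms is not a DLT. A patient who completes the DLT period, or discontinues for a drug-related AE, then counts as a non-DLT in the 3+3 rule and the primary rate. On average this is worth about 0.5 to 3.5 points of escalation probability, given assumed event rates of 0.5% to 2%, other-DLT rates of 5% to 20%, and independence. The case for change rests less on that average than on settling the classification before an event occurs, since a single event can change a cohort's reading.

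A reader might infer more than the documents support:
- That severe events would go unseen or that escalation would be forced. The SRC must review and decide first, and may hold, expand or stop.
- That stopping pembrolizumab at Grade 4 makes the event a DLT. Stopping the drug and limiting the SBRT dose are different decisions; the stopping rule shows only how seriously the protocol takes the event.
- That the dose recommendation is materially biased. No document gives a rate that would support this.

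The change is worth making, but the design does not depend on it.

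**What to change.** Add to the haematological list in Section 3.2.1, when the event falls within the 12-week DLT period and is possibly, probably or definitely related to the combination:

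- (a) Grade 4 anaemia, or any Grade 4 immune-related haematological event of clinical interest in Table 12;
- (b) any Grade 5 haematological event.

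Item (b) will rarely apply alone, but it removes any argument over a death. Do not add Grade 4 neutropenia or thrombocytopenia lasting more than 7 days: the threshold is debatable, and showing that duration would need blood tests between the 21-day visits.

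The cost is protocol wording, with no new assessments and no change to the 6 to 12 plus 12 patients. The downside is the fall in escalation probability shown above: a rare extra DLT may expand a cohort to six or stop it. Because there is no de-escalation (Section 3.2), at dose level 1 one added event plus one other DLT would terminate the trial under Section 3.5.1, item 5. The investigators should accept that consequence knowingly.

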## **Non-Haematologic:**

Any NCI CTCAE  $\geq 3$  grade non-haematological toxicity that is definitely, probably or possibly related to the combination of pembrolizumab and lung SBRT including the following:

[figure not shown]
- Increased MRC dyspnoea score  $> 2$  grades from baseline and/or acute dyspnoea grade  $\geq 4$  (or CTCAE dyspnoea grade  $\geq 3$ ) persisting for  $> 7$  days (including weekend).
- Pneumonitis/pulmonary infiltrates grade  $\geq 3$  persisting for  $> 7$  days (including weekend).
- Oesophagitis grade  $\geq 3$  persisting for  $> 7$  days (including weekend).
- Toxicity leading to interruption of radiotherapy for  $> 7$  days (including weekend).

Escalation to the next dose level will not proceed until the following criteria are satisfied by the SRC:

- If 0 out of 3 patients experience a DLT, escalation to the next dose level can proceed.
- If 1 out of 3 patients experiences a DLT, a further 3 patients will be recruited at that dose level.
  - If 1 out of 6 patients experiences a DLT, then escalation to the next dose level can proceed.
  - If  $\geq 2$  out of 6 patients experience a DLT, the MAD will have been reached. The RP2D will be the dose level prior to when the DLTs were observed or dose level 2 if no DLTs were observed.  
All patients in the expansion cohort will have lung SBRT dosed at the RP2D (see Figure 1).
- If 2/3 patients experience a DLT then the MAD will have been reached and the expansion cohort phase will begin at the previous dose level unless this occurs at dose level 1.
- If dose level 1 is not tolerated due to DLTs, the expansion cohort will not go ahead and the trial will be terminated.

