#### **3.5.1 Criteria for Early Trial Termination**

Early trial termination will be the result of the criteria specified below:

1. Quality or quantity of data recording is inaccurate or incomplete
2. Poor adherence to protocol and regulatory requirements

3. Incidence or severity of adverse drug reaction in this or other studies indicates a potential health hazard to patients
4. Plans to modify or discontinue the development of the study drug
5. If DLT is seen at dose level 1 in 2 out of 3 or 2 out of 6 patients

In accordance with the conditions of supply agreement with MSD, ample notification will be provided to the sponsor (via RM-CTU) and sites should alterations to the drug supply change. This is to allow time for appropriate adjustments to be made in regards to the patient's treatment.

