#### *Immune-mediated pneumonitis*

Monitor subjects for signs and symptoms of pneumonitis. If pneumonitis is suspected, evaluate with radiographic imaging and exclude other causes. Administer corticosteroids for Grade 2 or greater events (initial dose of 1-2 mg/kg/day prednisone or equivalent followed by a taper), withhold pembrolizumab for moderate (Grade 2) pneumonitis, and permanently discontinue pembrolizumab for recurrent moderate (Grade 2), severe (Grade 3) or life-threatening (Grade 4) pneumonitis.

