## 6.6 Supportive Care Guidelines for Pneumonitis

Patients with symptomatic pneumonitis should immediately stop receiving pembrolizumab and have an evaluation. The evaluation may include bronchoscopy and pulmonary function tests to rule out other causes such as infection. If the patient is determined to have study drug associated pneumonitis, the suggested treatment plan is detailed in Table 11.

**Table 11:** Recommended Approach to Handling Pneumonitis

Study drug associated pneumonitis	Withhold/Discontinue Pembrolizumab?	Supportive Care
Grade 1 (asymptomatic)	No action	Intervention not indicated
Grade 2	Withhold pembrolizumab, may return to treatment if improves to Grade 1 or resolves within 12 weeks Second episode of pneumonitis – discontinue pembrolizumab if upon re-challenge the patient develops a second episode of Grade 2 or higher pneumonitis.	Consider pulmonary consultation with bronchoscopy and biopsy/BAL. Conduct an in person evaluation approximately twice per week Consider frequent Chest X-ray as part of monitoring Treat with systemic corticosteroids at a dose of 1 to 2 mg/kg/day prednisone or equivalent. When symptoms improve to Grade 1 or less, steroid taper should be started and continued over no less than 4 weeks. Consider antibiotics
Grade 3 and Grade 4	Discontinue pembrolizumab	Hospitalise patient Bronchoscopy with biopsy and/or BAL is recommended. Immediately treat with intravenous steroids (methylprednisolone 125 mg IV). When symptoms improve to Grade 1 or less, a high dose oral steroid (prednisone 1 to 2 mg/kg once per day or dexamethasone 4 mg every 4 hours) taper should be started and continued over no less than 4 weeks. If IV steroids followed by high dose oral steroids does not reduce initial symptoms within 48 to 72 hours, treat with additional anti-inflammatory measures. Discontinue additional anti-inflammatory measures upon symptom relief and initiate a prolonged steroid taper over 45 to 60 days. If symptoms worsen during steroid reduction, initiate a re-tapering of steroids starting at a higher dose of 80 or 100mg followed by a more prolonged taper and administer additional anti-inflammatory measures, as needed add prophylactic antibiotics for opportunistic infections. The use of infliximab may be indicated as appropriate.

For Grade 2 pneumonitis that improves to  $\leq$  Grade 1 within 12 weeks, the following rules should apply:

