### 7.3.1 Determining AE Severity and Grade

AE severity and grade will be evaluated according to the NCI Common Terminology for Adverse Events (CTCAE), version 4.0. Any AE which changes CTCAE grade over the course of a given episode should be closed at the date the severity changed and a new AE recorded on the AE case report forms from that date at the new severity.

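### Section 3.2.1 gives two rules for a short-lived related grade 3 or higher dyspnoea, pneumonitis or oesophagitis, so the same event can count as a DLT or not

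*Combined protocol and SAP*

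**What the plan says.** Section 3.2.1 first requires every DLT to be at least possibly related to the combination. Under the non-haematological heading it then counts any CTCAE grade 3 or higher "grade non-haematological toxicity that is definitely, probably or possibly related to the combination of pembrolizumab and lung SBRT including the following". That line carries no duration.

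The entries beneath it do. The pneumonitis entry reads "Pneumonitis/pulmonary infiltrates grade $\geq 3$ persisting for $> 7$ days (including weekend", and the oesophagitis entry has the same form. The dyspnoea entry combines a rise in MRC score, acute dyspnoea of grade 4 or higher and CTCAE dyspnoea of grade 3 or higher, with a single condition of more than 7 days at the end. A fourth entry covers interruption of radiotherapy for more than 7 days.

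Section 3.2 fixes the window: "The DLT period for this study is 12 weeks from the last dose of lung SBRT". The DLT count then decides whether to escalate, add three patients or declare the maximum administered dose (MAD). Section 3.5.1 lists as a ground for ending the trial: "If DLT is seen at dose level 1 in 2 out of 3 or 2 out of 6 patients". Section 8.1.1 makes the proportion of patients with a DLT, with an exact binomial 95% interval, the primary analysis.

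Three other sections bear on the case. Section 6.5 says to "permanently discontinue pembrolizumab for recurrent moderate (Grade 2), severe (Grade 3) or life-threatening (Grade 4) pneumonitis", and Table 8 agrees for grades 3–4. Section 4.3 says: "A patient that discontinues the trial for a drug-related AE will not be replaced and will be counted in the evaluable population". Section 7.3.1 says: "Any AE which changes CTCAE grade over the course of a given episode should be closed at the date the severity changed".

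**The concern.** Take a related grade 3 or 4 pneumonitis that drops to grade 2 on day 5. Under the general line it is a DLT. Under its own entry it is not. If the general line governs, the 7-day wording on the CTCAE entries has no effect. If the entries govern, the word *including* is wrong.

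On the restrictive reading, a patient whose pembrolizumab has been permanently stopped for severe pneumonitis can sit in the denominator as DLT-free. The toxicities involved are central to this trial: section 6.1.2 lists pneumonitis, oesophagitis and dyspnoea as known effects of lung SBRT. With three to six patients per level, one reclassified patient can change the dose decision and the primary estimate.

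**Working it through.** **1. The text.** One event is set against each rule: related grade 3–4 pneumonitis, below grade 3 within 7 days.

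| Source | Result |
|---|---|
| 3.2.1, general line | DLT |
| 3.2.1, pneumonitis entry | not a DLT |
| 6.5 and Table 8 | pembrolizumab permanently stopped |
| 4.3, if the patient leaves the trial for it | not replaced, stays evaluable |

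Sections 3.2, 3.5.1, 4.3, 8.1.1 and 8.1.4 use the term DLT without defining it further. The MRC-score and radiotherapy-interruption criteria can capture events that are not CTCAE grade 3, so they add something on either reading. The conflict is confined to the three CTCAE entries.

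**2. Whether the case can arise.** Section 6.6 treats grade 3–4 pneumonitis with immediate intravenous steroids and adds treatment if this "does not reduce initial symptoms within 48 to 72 hours". Under 7.3.1 the grade 3 record closes on the day the grade changes. A record of grade 3 lasting less than 7 days is therefore possible. How often it would happen is not stated.

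**3. Effect on the decision.** This follows from the 3+3 rule and needs no assumed rate.
- 0/3 becomes 1/3: three more patients instead of escalation.
- 1/6 becomes 2/6: MAD instead of escalation, and termination at level 1.

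**4. Effect on the primary estimate.** The Clopper–Pearson limits for x events in n are the 0.025 quantile of Beta(x, n−x+1) and the 0.975 quantile of Beta(x+1, n−x).
- 1/6: 0.4% to 64.1%.
- 2/6: 4.3% to 77.7%.

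**5. Illustration of size.** The plan gives no target DLT rate and no operating characteristics to reproduce. Its only related figure, 6 to 12 escalation patients, is correct (2×3 and 2×6). The nearest anchors, in section 1.1.4.2, are for pembrolizumab alone: grade 3–5 events in 13–16% of patients, and grade 3–5 pneumonitis in 2%, whatever its duration. Neither refers to this trial's DLT window, and the rate with SBRT is unknown.

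Assume a total related grade 3 or higher rate of 15%, of which s = 1% or 2% of patients have only a short-lived listed event. With q = 1−p,

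P(MAD at one level) = 1 − q³ − 3pq²·q³.

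- General line, p = 0.15: 1 − 0.6141 − 0.3251×0.6141 = 18.6%.
- Restrictive, s = 1%, p = 0.14: 16.6%, a gap of 2.0 points.
- Restrictive, s = 2%, p = 0.13: 14.7%, a gap of 3.9 points.

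With totals of 13% and 16% the gaps for the same s run from 1.9 to 4.0 points. The chance of at least one such event in six patients, 1 − (1−s)⁶, is 5.9% or 11.4%.

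**The case against.** The strongest reply is that the plain wording already settles the matter. *Including* illustrates a rule and does not carve out exceptions, so every related grade 3 or higher event counts and the 7-day words are merely redundant. That is the more natural reading and also the cautious one. It does not explain why three entries carry a condition with no effect, and a site or committee could reasonably apply the entry that names the event. A figure is also missing from the available text between the general line and the list. It might reconcile them, so the point rests on what is visible.

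A reader might infer that the protocol leaves patients unprotected. The documents do not support that. Severe pneumonitis stops pembrolizumab whatever its DLT label. The Safety Review Committee, under an independent chair (10.9), reviews toxicities before each escalation. Section 3.5.1 also allows termination for the incidence or severity of reactions. What the committee lacks is a written rule for this event, and in an open-label trial it would be choosing the definition after seeing the case.

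A reader might also infer that short-lived events are likely. The 48–72 hour check in 6.6 concerns symptoms and does not show that grade 3 resolves within a week. Appendix 3 excludes central lesions and limits lung and oesophageal dose. Applying the illustration to the 12-patient maximum would overstate exposure. At a 15% rate, expected size per level is 3 + 3×0.325 = 3.98, and level 2 opens with probability 0.814, so about 3.98×1.814 = 7.2 patients are expected. Rates above 2% would exceed the only pneumonitis anchor, which is for any duration.

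**Conclusion.** Wrong as written, and worth correcting. Section 3.2.1 states two incompatible rules for one class of event, and the visible text does not rank them. The documents do not show that the restrictive reading was intended or would be applied.

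The change in decision and the shift from 1/6 to 2/6 follow directly from the protocol's rules. The gap of about 2–4 points in the chance of MAD, and the 6–11% chance of at least one such event in six patients, rest on an assumed 15% total and an assumed 1–2% share. They show scale only. Confidence is medium because of the missing figure.

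**What to change.** In 3.2.1:
- State that any related CTCAE grade 3 or higher non-haematological toxicity is a DLT whatever its duration.
- Remove the 7-day condition from the pneumonitis and oesophagitis entries.
- Redraft the dyspnoea entry, because one duration phrase now covers all its parts. Let it apply only to the MRC-score criterion, and let CTCAE dyspnoea of grade 3 or higher fall under the general line.
- Leave the radiotherapy-interruption criterion as it is.

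If the sponsor intends a duration exception, write it explicitly and limit it to grade 3 events that resolve to grade 2 or lower within 7 days, so that every related grade 4–5 event remains a DLT.

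The cost is a small wording amendment through the route in section 10.7 (Safety Review Committee, sponsor, ethics committee and, where required, the MHRA). No visits or assessments are added. The DLT count may be slightly higher than under the restrictive reading, which can mean expanding a cohort to six, within the planned maximum, or stopping escalation sooner.
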